10.2 Monitoring

The study will be monitored in accordance with applicable Chinese regulations and standard operating procedures. Throughout the study, the sponsor or designated personnel will monitor the conduct of the study sites to ensure the following:

- Data are accurate, complete, and reliable.
- The safety and rights of participants are protected.
- The study is conducted in compliance with the most recent version of the approved protocol, including the administration of the investigational treatment as per the protocol.
- The study adheres to all other study agreements and regulatory requirements.

Before data are entered into the eCRF, source documentation must be available. The monitor will verify whether the data entered into the eCRF is complete, in compliance with the protocol, and consistent with regulatory requirements. The monitor will compare the eCRF data with the original source data. All source documents must be maintained by the study site and must be available for review.

11. Study Management

11.1 Quality Control and Quality Assurance

Qualifications of Research Institutions: Clinical research institutions must be accredited and authorized to conduct pharmaceutical clinical trials.

Qualifications of Researchers: Researchers must undergo appropriate training and perform their tasks under the supervision of qualified professionals.

Laboratory Quality Control Measures: Laboratories must comply with relevant regulations and establish SOPs for experimental observation metrics and quality control procedures.

Clinical Research Quality Control Measures:

- (1) Prior to the commencement of the clinical trial, all researchers and study-related personnel at the research institutions must receive training on the study protocol.
- (2) All necessary equipment for the study must be fully operational, meet the required testing conditions, and be free from malfunctions. The equipment must undergo a preliminary testing phase to confirm its functionality.
- (3) Investigational products must be handled by designated personnel and stored according to the conditions outlined in the study protocol. Any remaining investigational products should be stored separately, with a detailed log of the remaining quantities, and returned to the sponsor upon completion of the study.

11.2 Document Retention

In compliance with relevant regulations, both the researchers and the medical institutions they are affiliated with must ensure that they have adequate facilities and conditions for storing essential clinical trial documents. The storage conditions must prevent direct exposure to light, be waterproof, and provide an environment conducive to the long-term preservation of documents. Additionally, document management policies and SOPs must be established.

Retained documents must be easily identifiable, accessible, retrievable, and properly organized. Any documents generated during the clinical trial that are not listed in the essential document management directory for each phase of the trial must also be included in the researchers' and institutions' essential document archives.

12. Responsibilities of All Parties and Other Relevant Provisions

12.1 Responsibilities of the Lead Study Institution

- (1) Design and develop the clinical study protocol and execute the clinical study protocol contract.
- (2) Provide relevant training to clinical research sites prior to the commencement of the study.
- (3) Prepare, compile, and maintain clinical data and documentation.
- (4) Develop, collect, and maintain relevant documents, including the clinical protocol, medical records, ethics committee approvals, adverse event reports, statistical analysis and raw data, and the final clinical report.
- (5) Ensure the documentation and reporting of adverse events to the appropriate regulatory authorities, and collaborate with clinical research sites to conduct study reviews.
- (6) Verify that research sites enroll participants in accordance with the established study protocol and procedures.
- (7) Monitor the enrollment progress at each research site.
- (8) Oversee the quality of data collection and reporting at each research site.
- (9) Collaborate with clinical research sites to evaluate the potential termination of the study when necessary.

12.2 Responsibilities of Clinical Research Sites (Study Centers)

- (1) Investigators must thoroughly review and comprehend the study protocol and adhere strictly to its guidelines.
- (2) Complete the clinical study within the prescribed timeline, in accordance with the established “Clinical Study Protocol,” including conducting in-person or telephone follow-up visits at the designated time points.

- (3) Submit the clinical study protocol to the relevant ethics committee for review, obtain feedback and suggestions, and communicate the results to the investigators.
- (4) Investigators must be fully familiar with the nature, mechanism of action, efficacy, and safety profile of the investigational drug.
- (5) Clinical studies must be conducted in medical institutions with adequate medical facilities, laboratory equipment, and appropriate staffing. The institution must be equipped to handle emergencies to ensure participant safety, and laboratory results must be accurate and reliable.
- (6) Investigators must obtain approval from the medical institution or relevant governing body to ensure sufficient time and resources to conduct the study within the specified timelines.
- (7) Investigators must ensure that participants are well-informed about the investigational drug and have sufficient time to consider participation in the study before providing written informed consent.
- (8) AEs occurring during the study must be accurately documented. Investigators must promptly notify the lead study institution and ethics committee of any SAEs within 24 hours of discovery and implement appropriate therapeutic measures. Investigators must swiftly assess any SAEs and take necessary actions to safeguard participant safety and rights.
- (9) Investigators must ensure that all clinical data, including medical records (such as photos and videos) and eCRFs, are recorded truthfully, accurately, completely, in a timely manner, and in compliance with legal and regulatory requirements.
- (10) Investigators must cooperate with monitoring and auditing activities conducted by the lead study institution to ensure the quality and integrity of the clinical study.
- (11) Investigators must ensure that the study does not conflict with or interfere with other concurrent clinical trials.
- (12) In the event of an emergency, the protection of participant welfare must take precedence. Investigators must assess whether it is necessary to deviate from

Statistical Analysis Plan

Efficacy and Safety of Memantine in the Treatment of Patients With Frequent Symptomatic Atrial Premature Beats: A Multicenter, Randomized, Double-Blind, Placebo- Controlled Study (STOP-AP)

Study drug:	Memantine Hydrochloride Tablets
Indications:	Frequent Symptomatic Premature Atrial Contractions
Document Type:	Statistical Analysis Plan
Version:	2.0
Release Date:	July 17, 2025

Document Revision History and Amendment Summary		
Version Number	Effective Date	Revision Summary
1.0	2025-02-14	Statistical Analysis Plan, Version 1.0 — Final
2.0	2025-07-17	
1. Removal of the planned interim analysis. An interim analysis for sample- size re- estimation had been prespecified after 128 participants completed the 6-week follow- up. At the planned interim time point, however, enrollment had already reached nearly 256 participants—the trial’s final target sample size. The Trial Steering Committee reviewed enrollment progress and unanimously resolved to cancel the prespecified interim analysis before unblinding. The trial remained fully blinded throughout, thereby preserving data integrity.
 
2. Addition of secondary endpoints:
 
a) The cumulative incidence of new-onset atrial fibrillation (AF) from baseline to Week 8: The proportion of participants who experience their first episode of AF lasting ≥ 30 seconds during any of the 4th, 6th, or 8th-week follow-up windows, with each participant counted only once, even if they have multiple occurrences across different follow-up windows.b) Efficacy analysis (e.g., $\geq 50\%$ reduction) for premature atrial contractions (PACs) or non- sustained atrial tachycardia (NSAT), based on the proportion of responders. 
3. Introduction of a subgroup analysis stratified by left- atrial diameter.

	
4. Revision of the secondary endpoint description from “incidence of new- onset sustained atrial tachycardia (SAT), AF, or atrial flutter (AFL) during consecutive 72- hour electrocardiogram (ECG) recordings at Weeks 4, 6, and 8” to “proportion of participants with new- onset SAT, AF, or AFL during consecutive 72- hour ECG recordings at Weeks 4, 6, and 8.”
 
5. Implementation of multiplicity- control procedures and inferential testing for the key secondary endpoints. Pre- specifying and reporting an appropriate multiplicity- control strategy preserves the family- wise type I error rate and reinforces statistical rigor. A hierarchical fixed- sequence testing procedure focuses on the most clinically relevant questions, thereby strengthening the confirmatory value and credibility of the conclusions without compromising participant safety or rights.
 
These amendments do not affect participant rights, safety information, or the trial data structure and were finalized before unblinding.

--	--

Catalogs

Statistical Analysis Plan.....	1
1. Trial Overview	1
1.1 Study Objectives	1
1.1.1 Primary Objective	1
1.1.2 Secondary Objective	1
1.2 Endpoints	1
1.2.1 Primary Endpoints	1
1.2.2 Secondary Endpoints	1
1.2.3 Safety Endpoints	2
1.3 Study Design	2
1.3.1 Overall Design	2
1.3.2 Sample- Size Determination	3
1.3.3 Randomization and Blinding	3
2. General Statistical Considerations	4
2.1 General Principles	4
2.2 Analysis Sets	4
2.3 Multicenter Design	4
2.4 Multiplicity Adjustment	5
3. Data Handling Principles	5
3.1 Derived Variables	5
3.1.1 Baseline and Change from Baseline.....	5
3.2 Missing Data	6
3.2.1 Incomplete or Missing Dates	6
3.2.2 Imputation of Missing AE Attributes	7
4. Statistical Analysis Methods	7
4.1 Study Population	7
4.1.1 Participant Disposition	7
4.1.2 Protocol Deviations	8
4.1.3 Demographic and Baseline Characteristics	8
4.1.4 PAC Diagnoses	8

4.1.5 Prior and Concurrent Medical History	9
4.1.6 Prior and Concomitant Drug Therapies	9
4.1.7 Prior and Concomitant Non- Drug Therapies	9
4.2 Efficacy Analysis	10
4.2.1 Primary Efficacy Analysis	10
4.2.2 Secondary Efficacy Endpoint Analysis	11
4.2.3 Subgroup Analysis	13
4.3 Safety Analysis	13
4.3.1 Drug Exposure	13
4.3.2 AE	14
4.3.3 Laboratory Evaluations	15
4.3.4 Vital Signs	16
4.3.5 12-Lead ECG	16
4.3.6 Symptom Assessment	16
4.3.7 NYHA Functional Class	16
4.3.8 SF-36 Health Survey	16
5. Planned Analyses	17
5.1 Interim Analysis	17
6. Deviations from the planned analysis in the protocol	17

1. Trial Overview

This Statistical Analysis Plan (SAP) specifies the statistical methods and data-handling procedures for the trial entitled “Efficacy and Safety of Memantine in the treatment of Frequent Symptomatic Atrial Premature beats: a multicenter randomized double-blind placebo-controlled study (STOP-AP)”.

The present SAP is based on Clinical Trial Protocol Version 2.3, dated 29 June 2025.

1.1 Study Objectives

1.1.1 Primary Objective

To evaluate the efficacy of memantine in treating frequent symptomatic PACs.

1.1.2 Secondary Objective

To assess the safety profile of memantine in patients with frequent symptomatic PACs.

1.2 Endpoints

1.2.1 Primary Endpoints

The percentage change from baseline in the 24-hour mean number of PACs at Week 6.

1.2.2 Secondary Endpoints

- a)** The change from baseline in the 24-hour mean number and burden of PACs at Weeks 4, 6, and 8;
- b)** The change from baseline in the 24-hour mean episode count and burden of NSAT at Weeks 4, 6, and 8;
- c)** The change from baseline in the 24-hour mean episode count of SAT, AF, and AFL at Weeks 4, 6, and 8;
- d)** The proportion of participants with new-onset SAT, AF, or AFL lasting ≥ 30 seconds during a consecutive 72-hour monitoring period at Weeks 4, 6, and 8. This endpoint will be calculated based on the first occurrence of SAT, AF, or AFL during the respective 72-hour monitoring windows;
- e)** The cumulative incidence of new-onset AF from baseline to Week 8: The proportion of participants who experience their first episode of AF lasting ≥ 30 seconds during any of the 4th, 6th, or 8th-week follow-up windows, with each participant counted only once, even if they have multiple occurrences across different follow-up windows ;

- f)** The change from baseline in the SF-36 quality of life score at Week 6;
- g)** Efficacy analysis of PACs or NSAT, based on the proportion of responders.

1.2.3 Safety Endpoints

The incidence of adverse events (including psychiatric symptoms, seizures, bradycardia and new-onset heart failure, etc.), serious adverse events, laboratory test abnormalities, and abnormal ECG findings.

1.3 Study Design

1.3.1 Overall Design

This investigator-initiated, multicenter, randomized, double-blind, parallel-group, placebo-controlled trial will enroll 256 adults (18–80 years of age) with frequent symptomatic PACs.

After an initial eligibility screen, all candidates will undergo 72-hour continuous patch-based ambulatory electrocardiographic monitoring to quantify baseline PAC burden. Participants who meet the inclusion criteria will be randomly assigned on Day 0, in a 1:1 ratio, to receive oral memantine or matched placebo. Randomization will be stratified according to age (≥ 65 vs. < 65 years) and baseline PAC burden (≥ 5000 vs. < 5000 PACs per 24 hours), yielding 128 participants per group (total, 256).

The protocol specifies five visits:

- Visit 1 (Screening; ≤ 14 days before randomization)—Baseline clinical assessments and 72-hour ambulatory ECG monitoring.
- Visit 2 (Day 7 ± 2 days)—Telephone contact to assess treatment adherence and solicit adverse events (AEs).
- Visit 3 (Day 28 ± 3 days), Visit 4 (Day 42 ± 3 days; end of treatment), and Visit 5 (Day 56 ± 3 days; end of study) — On-site evaluations, each including repeat 72-hour ambulatory ECG monitoring.

A schematic of the study procedures is provided in Figure 1.

[figure not shown]

Figure 1 Study Design Flowchart

The treatment phase will last 42 to 45 days. Seventy- two- hour ambulatory ECG will be initiated on study days 25–28 for Visit 3 (V3), days 39–42 for Visit 4 (V4), and days 53–56 for Visit 5 (V5). For V4, monitoring must begin 72 hours before the final scheduled dose; thus, if dosing concludes on day 42, monitoring must start on day 39. Conversely, if monitoring is initiated on day 42, study medication must continue through day 45. All other assessments scheduled for V3 – V5 must be completed between placement and removal of the 72- hour ECG device.

1.3.2 Sample- Size Determination

Based on the results of our preliminary exploratory single-arm study evaluating the efficacy of memantine in the treatment of PACs, the 24-hour mean reduction in PACs was 75.4%. Considering the robustness of results from the small-sample trial and potential sampling error, we conservatively estimated a 50% reduction in the 24-hour mean burden of PACs following treatment with memantine, while the placebo group is expected to show a 30% reduction, with a standard deviation of 35%. The dropout rate is assumed to be 15.0%. Using EAST 6.5 software for sample size calculation with a one-sided $\alpha = 0.025$ and a 1:1 allocation ratio between the memantine and placebo groups, a total of 256 participants will be enrolled, providing more than 95% power to detect the pre-specified between-group difference.

1.3.3 Randomization and Blinding

Eligible participants will be randomly assigned, in a 1:1 ratio, to receive either memantine or matching placebo. A stratified block design will be used, with randomization stratified by baseline 24-hour PAC burden (≥ 5000 vs. < 5000 PACs per 24 hours) and age (≥ 65 vs. < 65 years). An independent statistician who is otherwise unaffiliated with the study will generate the randomization list and corresponding treatment-allocation list with SAS software (version 9.4 or higher). Both lists will be uploaded to an interactive response technology (IRT) system, which will assign each participant a unique randomization number and the corresponding study-drug kit on Day 0. Randomization and kit numbers, once issued, will not be reused. Participants who withdraw from the study—irrespective of drug exposure—will not be re-enrolled.

2. General Statistical Considerations

2.1 General Principles

Unless otherwise specified, data will be summarized descriptively.

- Continuous variables: number of non-missing observations (n), mean, standard deviation, median, minimum, and maximum.
- Categorical variables: absolute frequency (n) and percentage (%).

2.2 Analysis Sets

- **Full Analysis Set (FAS)** — Includes all randomized participants who receive at least one dose of investigational product; analyzed in the treatment groups to which they were randomly assigned (intention-to-treat principle).
- **Per Protocol Set (PPS)** — Includes all randomized participants who received at least one dose of investigational product, underwent at least one post-baseline efficacy assessment, and had no major protocol deviations that could affect evaluation of the primary efficacy endpoints.
- **Safety Analysis Set (SS)** — Includes all randomized participants who received at least one dose of investigational product; safety endpoints are analyzed according to the treatment actually received.

2.3 Multicenter Design

All trial sites are located in China. Because no clinically meaningful site-to-site heterogeneity is expected, data from all centers will be analyzed in aggregate.

2.4 Multiplicity Adjustment

If the primary endpoint is statistically significant (two-sided $P < 0.05$), key secondary endpoints will be evaluated with a fixed-sequence testing procedure to control the family-wise type I error rate. Each endpoint will be tested at a two-sided α of 0.05, and testing will proceed down the hierarchy only while significance is maintained.

Testing hierarchy

- a) Week 6 responder rate for PACs ($\geq 50\%$ reduction).
- b) Change from baseline to Week 6 in NSAT burden.
- c) Cumulative incidence of new-onset AF from baseline to Week 8.
- d) Incidence of new-onset AF at Week 4.
- e) Incidence of new-onset AF at Week 6.
- f) Incidence of new-onset AF at Week 8.

If any endpoint fails to achieve significance, formal hypothesis testing will stop, and all remaining secondary endpoints will be summarized descriptively.

3. Data Handling Principles

3.1 Derived Variables

3.1.1 Baseline and Change from Baseline

Unless otherwise specified, *baseline* is defined as the last non-missing scheduled or unscheduled assessment obtained before the first dose.

- Change from baseline = baseline value – post-baseline value.
- Percent change from baseline = $(\text{baseline value} - \text{post-baseline value}) / \text{baseline value} \times 100\%$.

3.2 Missing Data

Unless explicitly stated, missing data will remain missing; no imputation will be performed.

3.2.1 Incomplete or Missing Dates

Imputation of AE Onset Dates

- Year missing (or entire date missing): No imputation will be performed; the AE will be classified as a treatment- emergent adverse event (TEAE).

- Year present, month and/or day missing: Impute according to the hierarchy below.

In all cases, the imputed date must not precede the informed- consent date; if it does, use the consent date instead.

a) Month and day both missing

- If the year matches the year of first study- drug administration, impute the onset date as the first- dose date.
- Otherwise, impute 1 January of the reported year.

b) Month missing only

- Determine the month using the rule for “month and day both missing.

c) Day missing only

- If the reported year and month match those of first dosing, impute the day as the first- dose date.

- Otherwise, impute the day as the first calendar day of the reported month.

Imputation of Adverse- Event (AE) End Dates

- For incomplete end dates, impute the last calendar day of the reported month; if both month and day are missing, impute 31 December of the reported year.

- Participants who die: If the imputed end date falls after the date of death, replace it with the death date.

- Participants alive at study completion or data cutoff: If the imputed end date exceeds the last known contact date or the data- cutoff date, replace it with the earlier of those two dates.

Imputation Rules for Start and End Dates of Prior and Concomitant Medications and Non- Drug Therapies

If the year is missing—or the complete date is missing—for either the start or end date, no imputation will be performed; the exposure will be classified as concomitant.

When the year is present but the month and/or day are missing, dates will be imputed as follows:

- Start date recorded as year + month only: impute the first day of that month.
- Start date recorded as year only: impute 1 January of that year.
- End date recorded as year + month only: impute the last day of that month.
- End date recorded as year only: impute 31 December of that year.

Consistency Checks

- If the imputed end date exceeds the participant's date of death, replace it with the date of death.
- If the participant is alive at study completion or data cut-off and the imputed end date exceeds either the last known contact date or the data-cut-off date, replace it with the earlier of those two dates.

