Score 1: Mild symptoms, occasional palpitations that do not affect daily life;

Score 2: Moderate symptoms, frequent palpitations, mildly interfering with daily life;

Score 3: Severe symptoms with persistent palpitations that significantly interfere with daily life;

4. Basic information including height, weight, waist circumference, education level, etc;

5. Past medical history: hemorrhagic/ischemic stroke, transient ischemic attack, myocardial infarction, history of epilepsy or seizures, and psychiatric disorders;

6. History of prior medications: medication use within 4 weeks prior to screening; history of non-drug therapy (including surgery): history of non- drug therapy within 6 months prior to screening; collection of a full history of prior cardiac-related surgery;

7. Vital signs include temperature, blood pressure, pulse, and respiration;

8. Including routine blood, liver function (alanine aminotransferase, glutamic aminotransferase, gamma glutamyl transpeptidase, total bilirubin, direct bilirubin, indirect bilirubin), thyroid function (fT3, fT4, TSH), renal function (creatinine, urea nitrogen or urea, glomerular filtration rate), electrolytes (blood sodium, potassium, magnesium, calcium), blood lipids (total cholesterol, triglyceride, HDL cholesterol, LDL cholesterol ester), fasting blood glucose, glycated hemoglobin, NT-pro BNP (preferred) or BNP.

9. Female subjects of childbearing age should undergo blood or urine HCG test to exclude pregnancy.

10. The duration of drug administration in this study was 42-45 days, and the start time of 3-day (72h) ECG recorder monitoring for V3~V5 visits was D25~D28 for V3, D39~D42 for V4, and D53~D56 for V5, respectively. ECG monitoring for the V4 visit should be started 3 days prior to the end of the drug administration, and the 3 consecutive days (72h) of ECG recorder monitoring should be performed at D39, if the administration of drug was ended at D42. recorder monitoring needs to be performed at D39. If 3 consecutive days (72h) of ECG monitoring is performed at D42, the drug must be administered until D45; other operations for V3~V5 visits are performed from the day of the 3-day ECG monitoring on to the day of the removal of the ECG recorder.

Table 5 Specific requirements for each inspection item

Inspection item	Requirements and observables
vital signs	Temperature, blood pressure, pulse, respiration.

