4.1.6 Prior and Concomitant Drug Therapies

Within the FAS, prior and concomitant medications will be summarized descriptively by treatment group. Prior and concomitant drug therapies will be coded with the WHO Drug Dictionary Global and tabulated by Anatomical Therapeutic Chemical (ATC) level-2 category and Preferred Name (PN). ATC level-2 categories and PNs will be ranked in descending order of overall frequency, with alphabetical ordering applied to ties. A participant-level listing of every prior and concomitant drug therapies will be provided.

Prior drug therapies — any drug therapies that occurred before the first study dose (i.e., the stop date precedes the first-dose date).

Concomitant drug therapies — any drug therapies that meets either of the following criteria: initiated on or after the first-dose date, or initiated before the first-dose date and continuing on or after that date.

Missing or incomplete start- or stop- date information will be imputed according to the procedures outlined in Section 3.2.

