4.1.7 Prior and Concomitant Non- Drug Therapies

Within the FAS, all non-drug interventions administered before or during the trial will be summarized descriptively by treatment group. Each intervention will be coded with the MedDRA and tabulated by SOC and PT. SOCs and PTs will be ranked in descending

order of overall frequency, with alphabetical ordering applied to ties. A participant- level listing of every prior and concomitant non- drug therapy will also be provided.

- **Prior Non- Drug Therapy:** an non- drug intervention completed before the first administration of study drug (i.e., the stop date precedes the first- dose date).

- **Concomitant Non- Drug Therapy:** an non- drug intervention that either (i) is initiated on or after the first- dose date or (ii) is initiated before the first- dose date and continues on or after that date.

Missing or partial start- or stop- date information will be imputed according to the procedures described in Section 3.2.

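### SAP 3.2.1 classes a therapy with a missing start year as concomitant even when a known stop date before first dose makes it prior under SAP 4.1.6 and 4.1.7

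*SAP*

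**What the plan says.** Three parts of the SAP bear on this.

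- **Missing-date rule (SAP 3.2.1, medications and non-drug therapies).** When the year or the complete date is absent for "either the start or end date, no imputation will be performed; the exposure will be classified as concomitant". When the year is present, partial dates are filled in: starts to the earliest possible day, stops to the latest.
- **Drug definitions (SAP 4.1.6).** Prior means "any drug therapies that occurred before the first study dose (i.e., the stop date precedes the first-dose date". Concomitant means "initiated on or after the first-dose date, or initiated before the first-dose date and continuing on or after that date". The section then says that missing or partial date "information will be imputed according to the procedures outlined in Section 3.2".
- **Non-drug definitions (SAP 4.1.7).** Prior means "completed before the first administration of study drug", again judged by the stop date. Missing or partial date "information will be imputed according to the procedures described in Section 3.2".

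On what is collected, the notes to the flow table in Protocol 6.1 specify: "History of prior medications: medication use within 4 weeks prior to screening".

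**The concern.** Under the definitions, the start date plays no part in deciding whether a therapy is prior. If it stopped before first dose, it is prior. The missing-date rule nevertheless lets an unknown start year settle the class and disregards a stop date that is on file. A record can therefore be prior under one section and concomitant under another.

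What is at stake is the accuracy of the concomitant-therapy tables. Protocol 5.7 restricts antiarrhythmics during the study, and Protocol 5.8 allows bisoprolol for intolerable symptoms. The primary model in SAP 4.2.1 has no term for such use, so the tables and listing under SAP 4.1.6 are the main planned place where a reader would look for it. Those tables go down to Preferred Name. Bisoprolol stopped before screening, with an unknown start year, would be counted in the same row as bisoprolol begun on study.

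**Working it through.** The plan states no figure here, so the check is a comparison of rules.

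**Step 1. Cross the dates.** Let the start and the stop each be year missing, before first dose, or on/after first dose. That gives 3 × 3 = 9 combinations. Start on/after with stop before is impossible, which leaves 9 − 1 = 8.

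| Start | Stop | SAP 3.2.1 applied | SAP 4.1.6 / 4.1.7 definitions | Result |
|---|---|---|---|---|
| missing | missing | concomitant | cannot decide | default needed |
| missing | before | concomitant | prior | **conflict** |
| missing | on/after | concomitant | concomitant | agree |
| before | missing | concomitant | cannot decide | default needed |
| before | before | prior (no year missing, so the definitions apply) | prior | agree |
| before | on/after | concomitant (same reason) | concomitant | agree |
| on/after | missing | concomitant | concomitant | agree |
| on/after | on/after | concomitant (same reason) | concomitant | agree |

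The count is 1 conflict + 2 undecidable + 5 in agreement = 8.

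**Step 2. Does another rule correct the conflict?** No. The consistency checks in SAP 3.2.1 only cap imputed end dates at death, last contact or data cut-off. SAP 4.1.6 and 4.1.7 send incomplete dates back to Section 3.2 and make no exception for a known early stop.

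**Step 3. Can such a record arise?** Exclusion (5) in Protocol 4.2 bars amiodarone within 4 weeks of screening and other antiarrhythmics within 1 week. Prior drugs are collected for 4 weeks before screening. The span in which a stopped drug is both permitted and collected is therefore:

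- other antiarrhythmics: 4 − 1 = 3 weeks (stopped about 1 to 4 weeks before screening);
- amiodarone: 4 − 4 = 0 weeks, so it is at most a borderline case.

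The Background in the protocol describes beta-blockers as an option for symptomatic PACs, so earlier beta-blocker use is plausible in this population. For a non-amiodarone agent the stop date should be on file, because eligibility depends on it.

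**Step 4. What changes if a known stop date decides?** Only the conflict row, from concomitant to prior. The other seven rows stay as they are. This also holds for stop dates imputed from a known year: SAP 3.2.1 moves a partial stop to the last day of the month or year, so an imputed stop before first dose means that the therapy did end before first dose.

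**The case against.** The strongest defence is that this is an ambiguity and not an error. No sentence gives SAP 3.2.1 precedence, and a programmer who sees a complete pre-dose stop date could follow SAP 4.1.6. That is possible. But a record without a start year has incomplete date information, SAP 4.1.6 sends it to Section 3.2, and the rule there is explicit. Two programmers could follow the SAP and get different tables.

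The second defence is that defaulting to concomitant is conservative and matches the SAP's handling of adverse events with no onset year. This stands for the two undecidable rows. It does not stand where the stop date already answers the question.

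The third is that few records will be affected. The year must be wholly absent, since a year alone is enough for imputation to 1 January, and the collection window is short. This stands: the documents do not say how often a start year is missing, and no count can be derived.

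A reader might infer three stronger consequences that the documents do not support.

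- **Old operations listed as on-study treatment.** The protocol does ask for "collection of a full history of prior cardiac-related surgery" with no time limit. But a one-off procedure with an unknown year will usually lack both years. That is an undecidable row, where the default is reasonable, and not the conflict row.
- **Exclusions from the per-protocol set.** Nothing derives protocol deviations from this classification. SAP 4.1.2 has them listed and graded before database lock, and Protocol 10.1 has a data review meeting settle the analysis populations.
- **A hidden difference in rescue use.** Protocol 5.6 requires dates for drugs given from consent onward, and the participant-level listing allows a check. Drug history from before randomization should be balanced between arms in expectation. Stray entries would add noise and pull a ratio towards one, but would not systematically shift the absolute difference.

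**Conclusion.** The contradiction is real and narrow. SAP 3.2.1 disagrees with SAP 4.1.6 and 4.1.7 in one of eight date combinations: start year missing with a known stop date before first dose. Applied as written, it counts a therapy that had ended as on-study treatment and may mix it with true rescue use under one Preferred Name.

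The effect is limited to the descriptive tables under SAP 4.1.6 and 4.1.7. The primary ANCOVA, multiple imputation, MMRM, testing hierarchy and subgroup analyses do not use the prior/concomitant class. The number of affected records is unknown. The conclusion rests on the literal wording and on the assumption that some participants have a recorded stop date but no start year. Severity is minor.

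**What to change.** In SAP 3.2.1, replace the missing-year rule for medications and non-drug therapies with wording to this effect: a stop date before first dose, whether complete or imputed from a known year, makes the therapy prior whatever the start date; where the year of either date is missing and the available dates or an ongoing flag cannot show that the therapy ended before first dose, the therapy is classed as concomitant.

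This brings the rule into line with SAP 4.1.6 and 4.1.7, which need no edit. The cost is one sentence and one programming condition, ideally before database lock. It needs no new data and changes no inferential analysis.
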